9.4.3 ANALYSIS OF THE SECONDARY ENDPOINT(S)

Our secondary goal is to test if rTMS improves also the quality of AVH (BAVQ-R), positive symptoms (BPRS-subscale), general psychopathology (CGI), and global functioning (GAF). Further, we want to confirm that rTMS has no impact on cognitive functions (rBANS).

Therefore, we will compute a number of repeated ANCOVAs with time of measurements as the within-subject factor, group (treatment vs. placebo) as between subject's factor, and baseline BAVQ-R scores, the positive symptom BPRS-scale, the CGI, and GAF scores as covariates, respectively. Patients who drop out of the study will not be included in the analyses. Further, we will compare the rBANS scores of baseline with the outcome scores within patients.

Additionally, we want to test if baseline neuroimaging biomarkers can predict response to rTMS. Therefore, voxel-wise multiple regression analyses in our neuroimaging measures will be performed to reveal areas and networks which correlate with the baseline scores of the HCS. We will calculate structural and functional connectivity analyses.

Preprocessing, and overview of the neuroimaging measures:

Baseline metabolic neuronal activity

The treatment effect will be monitored by assessing the baseline resting metabolic neuronal activity measured by ASL (Philipp Homan et al., 2011; Kindler et al., 2012; Orosz et al., 2012). Additionally, variations in resting CBF may be used as covariates of nuisance in all the analysis steps described so far.

The perfusion images will be pre-processed and analyzed with FSL 5.0. First, the raw pCASL data undergo pre-processing that includes motion-correction with MCFLIRT (Jenkinson, Bannister, Brady, & Smith, 2002), outlier-detection, and removal (Jenkinson et al., 2002; Jenkinson & Smith, 2001). Second, in order to create a mean difference map for each subject, control-tag pairwise differences are computed. These maps are normalized by the equilibrium magnetization (M0) of arterial blood estimated via the magnetization of CSF. Third, Bayesian Inference for Arterial Spin Labeling MRI (BASIL) (M. A. Chappell, Groves, Whitcher, & Woolrich, 2009) is employed to calculate resting state perfusion which provides blood flow in absolute units ([ml/100g/min]) with the following parameters: BAT = 1.3, TR = 3.5, TE = 1.8, T1 (blood) = 1.65 s, and alpha = 0.85. The application of a GM mask and partial volume correction (M. Chappell et al., 2011) ensures that only GM voxels are included in the CBF calculation. Fourth, the perfusion images are spatially normalized and transformed into MNI space using FLIRT (Jenkinson et al., 2002; Jenkinson & Smith, 2001) and FNIRT (Andersson, Jenkinson, & Smith, 2007), and then spatially smoothed with a 6 mm FWHM Gaussian kernel.

Resting state networks (RSN, BOLD fMRI)

Brain function is thought in terms of complex circuits that are optimized both for segregated and distributed information processing. These circuits can be studied with a task or at rest (Fair et al., 2007; Fox et al., 2005; Raichle & Snyder, 2007). The most studied functional connectivity network at rest is the default mode network (DMN) which may be investigated using BOLD fMRI time-series and quantified CBF time-series (Kay Jann, Koenig, Dierks, Boesch, & Federspiel, 2010; Orosz et al., 2012). In psychiatric population it may be of special interest to investigate the neurophysiological mechanism of hallucinations in patients because they do not need to actively respond to a task (i.e. resting state network/RSN). Resting-state neural activity can originate from the interplay between the local neural dynamics and the

large-scale structure of the brain (Cabral, Hugues, Sporns, & Deco, 2011). Interestingly, RSN were found to be altered in disease population as compared to healthy controls (Bassett, Nelson, Mueller, Camchong, & Lim, 2012), indicating that the quantitative assessment of RSN may be a potential method for investigating psychiatric diseases (Meda et al., 2012) including schizophrenia (Ma, Calhoun, Eichele, Du, & Adali, 2012; Venkataraman, Whitford, Westin, Golland, & Kubicki, 2012). Of special interest for the current proposal will be the investigation of the language related functional network, also termed “working memory” or “language network” (Catani et al., 2011; Friederici, 2011; Friederici, Brauer, & Lohmann, 2011; K. Jann et al., 2012; Morgan, Mishra, Newton, Gore, & Ding, 2009).

Network connectivity is assessed through the measure of correlation coefficient (Zalesky, Fornito, & Bullmore, 2012). fMRI-BOLD image processing will be performed within SPM8 (<http://fil.ion.ucl.ac.uk>) and will include 3-D motion detection and correction using Levenberg-Marquarts’s least square fit for six spatial parameters, slice scan time correction through Sinc-interpolation. Co-registration of 2-D functional and 3-D structural measurements will be performed and normalization of data will lead to images in standard MNI space. All fMRI time-series will be further analyzed within the framework of Independent Component Analysis (ICA) using the Group ICA Toolbox (GIFT software) (Calhoun, Adali, Pearlson, & Pekar, 2001). We will compute subject maps (SMs) will be computed and identify temporally coherent networks (TCNs) by estimating maximally independent spatial sources. Finally, we will use a back-reconstruction method based on PCA compression and projection to estimate subject-specific SMs and TCNs for rest separately for all sessions (Erhardt et al., 2011). A subsequent t-test for the beta values corresponding to the rest and TMS condition will be computed (Arbabshirani, Havlicek, Kiehl, Pearlson, & Calhoun, 2013).

Structure of gray and white matter properties

To investigate the structural properties of GM and WM the 3D structural T1 and DTI measurements will be used. T1 images will be used to define the regions of interest (ROI) for both structural and functional connectivity analyses. The ROIs will comprise cortical regions in the STG and superior temporal sulcus (STS, Brodmann areas/BA 41, 42 and 52) and in the subcortical thalamic area (medial geniculate body of thalamus/MGB).

With regard to structural connectivity analyses, diffusion tensor images will be used to compute fractional anisotropy (FA) values for further use in a voxel-wise statistical analysis, which will be conducted using Tract-Based Spatial Statistics (TBSS) (Smith et al., 2006); part of FSL (Smith et al., 2004) (version 5.0). FA maps are created by fitting a tensor model to the raw diffusion data using the FMRIB diffusion toolbox. Subsequently, a brain extraction tool will remove all non-brain parts of the image (Smith, 2002). All subjects’ FA data will be coregistered to a 1 mm × 1 mm × 1 mm Montreal Neurological Institute (MNI) standard space. This step will be performed using a non-linear registration tool FNIRT (FMRIB’s Non-Linear Image Registration Tool), which uses a B-spline representation of the registration warp field (Rueckert et al., 1999). Additionally, a mean FA image will be created and thinned in order to create a mean FA skeleton that represented the centers of all tracts common to the group. A lower FA threshold of 0.2 will be used to prevent the inclusion of non-skeletal voxels (Smith et al., 2006). Each subject’s aligned FA data will then be projected onto this skeleton. The resulting data will be analyzed using voxel-wise cross-subject statistics including a randomization tool, which is a simple permutation program that allows modeling and inferences within the framework of GLM-setup and is based on non-parametric inference methods (Nichols & Holmes, 2002).

Concerning functional connectivity analyses, the ROIs will be used as seed regions to compute the functional connectivity from these regions to other cortical brain regions using the Conn toolbox, a MATLAB-based cross-platform mapping software (www.nitrc.org/projects/conn). Further, GM analyses will be performed using voxel-based morphometry (VBM) (Good et al., 2001). VBM will be computed within the statistical parametric mapping (SPM8: <http://www.fil.ion.ucl.ac.uk/spm/>). Cortical thickness will be estimated using FreeSurfer (<http://surfer.nmr.mgh.harvard.edu>).

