3 OBJECTIVES AND ENDPOINTS

OBJECTIVES	ENDPOINTS	JUSTIFICATION FOR ENDPOINTS
Primary		
Examine the efficacy of low-frequency rTMS for the treatment of AVH in patients with a schizophrenia spectrum disorder.	Our primary outcome will be the score of the Hallucination Change Scale (HCS) (Hoffman et al., 2003). Response criteria: a) Clinically significant improvement in AVH is	The HCS is used as our primary outcome measure. The scale will be anchored at baseline using the narrative description of AVHs provided by the patient for the prior 24 hours, which will be assigned a score of 10. For subsequent assessments, the HCS ranges from 0-20 (with a score of 20

OBJECTIVES	ENDPOINTS	JUSTIFICATION FOR ENDPOINTS
	defined as a score of <8 on the HCS (Hoffman et al., 2013) b) Drop-outs: defined as patients who discontinue treatment before completing the 4 rTMS sessions.	corresponding to hallucinations twice as severe as baseline) (Hoffman et al., 2003; Hoffman et al., 2013). The HCS is a frequently used assessment for AVH in schizophrenia (Hoffman et al., 2003; Hoffman et al., 2013; Philipp Homan et al., 2011; P Homan et al., 2012). It is a feasible and time-efficient measure to assess severity of AVH on a daily basis and to evaluate improvement of AVH severity.
Secondary		
Monitor qualitative changes in AVH during the course of the rTMS treatment.	a) the qualitative content of AVH are assessed using the BAVQ-R to monitor changes in the content of AVH.	The BAVQ-R (CHADWICK, LEES, & BIRCHWOOD, 2000) is a self-report measure of patient's beliefs, emotions and behavior about AVH. This allows to assess changes in the quality of AVH over time and monitor if severity increases to the point of being dangerous for the patient or others (suicidal or homicidal tendencies).
Assessment of AVH as part of positive symptoms.	b) positive symptoms BPRS-subscale including "Hallucinatory Behavior", "Conceptual Disorganization", "Suspiciousness", and "Unusual Thought Content".	The positive symptoms BPRS-subscale is a well validated, often in studies used measure to assess positive symptoms including AVH (Robinson et al., 2015; Shafer, 2005).

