Examine the effects of rTMS on the global functioning of the patient with a schizophrenia spectrum disorder.	c) global function is assessed using the Clinical Global Impression (CGI) and the General Assessment of Functioning (GAF)	The global scores (CGI (Haro et al., 2003) and GAF (Jones, Thornicroft, Coffey, & Dunn, 1995)) nicely complement the specific measure and provide a complete picture of the patient's mental state.
Confirm that rTMS has no cognitive side effects.	d) The neuropsychological test Repeatable Battery for the Assessment of Neuropsychological Status (rBANS)	In order to confirm that rTMS has no undesirable cognitive side effects the rBANS is used as a standard cognitive measure.

Neurophysiological changes using magnetic resonance imaging (MRI) are investigated as predictors for rTMS treatment response.

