8 STUDY ASSESSMENTS AND PROCEDURES

8.1 EFFICACY ASSESSMENTS

Rating

All assessments will be performed by trained raters.

Time frame

Screening procedures / evaluation must be done on the same day or the day before inclusion of the patient into the study. The reason for this is that we assess rTMS effect independently of potentially influencing antipsychotic medication effects. Therefore, patients cannot start with antipsychotic medication treatment parallel to the rTMS treatment. Clinical interviews will be conducted by trained staff.

Imaging

MRI acquisition will consist of the following: On the day of imaging, the patient will be transported to the North Shore University Hospital 3T Siemens Prisma MRI suite. The patient will undergo an approximately 55 minutes long acquisition session. All subjects will receive structural (e.g., T1) and functional (e.g. resting BOLD fMRI, DTI, and ASL) MRI exams. During the anatomical images, the participating subject will be asked not to move, during resting state fMRI, the subject will be asked to open their eyes and to think of nothing in particular, but to stay awake. The total scanning time will be approximately 55 minutes.

Assessment of instruments

The primary outcome measure is the improvement of AVH measured with the HCS.

The secondary outcome measures are:

- Qualitative outcome of the BAVQ-R
- AVH as part of positive symptoms measured with the respective BPRS-subscale
- Global functioning assessed using the CGI and GAF
- Cognitive functioning assessed using the rBANS

Structural and functional neurophysiological characteristics are investigated as predictors for rTMS treatment response.

Outcome criteria

Responder criteria:

- a. Clinically significant improvement is defined as a score of <8 on the HCS (Hoffman et al., 2013)
- b. Drop-outs: defined as patients who discontinue treatment before completing the 4 rTMS sessions.

Premature exits:

- a. Consent for study participation is withdrawn before 4 rTMS treatments have been administered, or
- b. rTMS is discontinued for clinical or other reasons before 4 rTMS have been administered, or
- c. Patient misses more than two treatments in total.

Both drop-outs and premature exits in this study will be analyzed as last observation carried forward.

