9 STATISTICAL CONSIDERATIONS

9.1 STATISTICAL HYPOTHESES

Primary Efficacy Endpoint(s):

H0: Real rTMS has no superior effect over sham rTMS in reducing severity of AVH in schizophrenia (HCS score).
H1: Real rTMS has a superior effect over sham rTMS in reducing severity of AVH in schizophrenia (HCS score).

Secondary Efficacy Endpoint(s):

1. H0: Real rTMS has no superior effect over sham rTMS in reducing quality of AVH in schizophrenia (BAVQ-R score).
H1: Real rTMS has a superior effect over sham rTMS in reducing quality of AVH in schizophrenia (BAVQ-R score).
2. H0: Real rTMS has no superior effect over sham rTMS in reducing positive symptoms including AVH in schizophrenia (BPRS-subscale).
H1: Real rTMS has a superior effect over sham rTMS in reducing positive symptoms including AVH in schizophrenia (BPRS subscale).
3. H0: Real rTMS has no superior effect over sham rTMS in reducing severity of general psychopathology in schizophrenia (CGI score).
H1: Real rTMS has a superior effect over sham rTMS in reducing severity of general psychopathology in schizophrenia (CGI score).
4. H0: Real rTMS has no superior effect over sham rTMS in reducing global functioning in schizophrenia (GAF score).
H1: Real rTMS has a superior effect over sham rTMS in reducing global functioning in schizophrenia (GAF score).
5. H0: Real rTMS compared to sham rTMS does not impact cognitive functioning (RBANS).

H1: Real rTMS compared to sham rTMS does not impact cognitive functioning (RBANS).

6. H0: Response to rTMS is not predicted by neurophysiological characteristics.

H1: There are specific neurophysiological markers that predict response to rTMS.

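### The test of hypothesis 6 (markers that predict response to rTMS) specifies no arm or marker-by-arm term; if only its unusable HCS variable is corrected, a purely prognostic marker could be labelled a predictor of rTMS response

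*Combined protocol and SAP*

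**What the plan says.** The alternative in secondary hypothesis 6 (section 9.1) is "There are specific neurophysiological markers that predict response to rTMS". Section 9.4.3 takes this up with the aim "Additionally, we want to test if baseline neuroimaging biomarkers can predict response to rTMS" and then gives the method: "voxel-wise multiple regression analyses in our neuroimaging measures will be performed" in order "to reveal areas and networks which correlate with the baseline scores of the HCS".

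Section 3 explains how the HCS is anchored. The baseline description of the voices is the one "provided by the patient for the prior 24 hours, which will be assigned a score of 10". Response is defined in section 8.1: "Clinically significant improvement is defined as a score of <8 on the HCS". That definition does not enter the marker analysis.

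Group is a between-subject factor in the repeated-measures ANCOVAs for the HCS (9.4.2) and for the other clinical scales (9.4.3). It is not mentioned for the marker regression. Section 9.4.1 gives age and sex as examples of covariates. The one further imaging test that 9.4.3 spells out, a t-test between the rest and TMS conditions, does not relate a marker to response by arm. Sub-group analyses (9.4.7) and exploratory analyses (9.4.9) are marked N/A.

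On timing, the Synopsis objectives and 9.4.3 speak of baseline imaging as the predictor. One sentence, which appears in both the Synopsis and section 3, says instead: "Neurophysiological changes using magnetic resonance imaging (MRI) are investigated as predictors for rTMS treatment response".

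**The concern.** A marker that predicts response to rTMS is one for which the benefit of real over sham stimulation depends on the marker's value. A marker that merely accompanies a better or worse course, whichever arm the patient is in, is prognostic. Patients on sham may change too, so an association between a marker and outcome cannot tell the two apart unless the arms are compared.

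The trial collects what is needed: both arms are scanned and rated before and after treatment (sections 1.2, 4.1 and 9.3). The plan does not say that the sham arm will be used for this purpose. Prediction markers are in the trial's title, and a follow-up study in a larger sample is foreseen (9.2). A prognostic marker reported as predictive could send that study in the wrong direction.

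**Working it through.** **The plan's own figure.** The documents give no sample size for hypothesis 6. The only one is for the primary comparison: effect size 0.9, 80% power, alpha 5%, 20 per arm (9.2). By the normal approximation, two-sided, n per arm = 2 × (1.96 + 0.8416)² / 0.9² = 19.4, so 20 per arm and 40 in total. The two-sample t calculation gives 20.39 per arm, and power at 20 per arm is 79.2%. The stated 40 is reproduced to within rounding, and 20 per arm is used below.

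**Step 1: the analysis as written.** Baseline HCS is 10 for everyone, so its variance is 0. A correlation divides by the standard deviation of each variable and is therefore undefined. In a regression, a constant predictor cannot be separated from the intercept, and a constant outcome leaves nothing to explain. No marker can be declared, prognostic or predictive.

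**Step 2: correct the outcome only.** Inputs: 20 per arm and a real-sham difference of 0.9 SD (9.2); one marker, two-sided tests. The marker-outcome correlation r is not in the documents and is assumed. Model for each patient:

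outcome = 0.9 × arm + r × marker + √(1 − r²) × noise,

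with marker and noise standard normal and the same r in both arms. Such a marker is purely prognostic. Share of simulated trials in which it is significant at p < 0.05:

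| Assumed r, both arms | Pooled, no arm term | Pooled, arm as covariate | Real arm only | Marker-by-arm term |
|---|---|---|---|---|
| 0.3 | 41% | 47% | 25% | 5% |
| 0.4 | 66% | 74% | 45% | 5% |
| 0.5 | 86% | 91% | 64% | 5% |

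Adding arm as a covariate does not help. It removes noise and makes the prognostic association easier to see.

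**Step 3: a stricter threshold.** The planned analysis is voxel-wise, so p < 0.05 on a single marker is lenient. At an illustrative p < 0.001 (an assumption), the pooled rate is about 5% at r = 0.3 and 37% at r = 0.5. In the real arm alone it is about 2% and 13%.

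**Step 4: a marker that acts only under sham.** With r = 0.5 under sham and 0 under real rTMS, p < 0.05, the pooled analysis flags it in 31% of trials and the real-arm-only analysis in 5%.

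**Step 5: what the interaction can detect.** For a marker acting only under real rTMS:

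| Assumed r under real rTMS (0 under sham) | Power, p < 0.05 | Power, p < 0.001 |
|---|---|---|
| 0.5 | 34-36% | about 4% |
| 0.6 | 48% | about 8% |
| 0.7 | 64-65% | about 15% |

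Ranges reflect separate simulation runs. As an analytic check, the Fisher-z comparison of two correlations has power Φ(atanh(r) / √(2/17) − 1.96). For r = 0.5 this is Φ(0.549/0.343 − 1.96) = Φ(−0.36) = 36%; for 0.6 and 0.7 it gives 52% and 72%. The number per arm for 80% power at p < 0.05, 2 × (2.8016 / atanh(r))² + 3, is 56, 36 and 24. Put differently, at 20 per arm the interaction reaches 80% power (noncentral t, 36 df) only for a slope difference of about 0.91 residual SD per SD of marker. With no slope under sham, that corresponds to r = 0.91 / √(1 + 0.91²) = 0.67 under real rTMS.

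**The case against.** A reader might infer that the trial as planned will name false predictors. The documents do not support that. The written regression uses a constant and can name nothing, so the rates above describe a plan in which the outcome has been repaired and the model has not.

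A reader might also infer that the plan tests by simple correlation or rules the sham data out. It does not. The method is multiple regression and the covariate list in 9.4.1 is open. The plan is silent on arm, which is a failure to specify and not an exclusion. The silence still matters: group is named for every ANCOVA and nowhere for the markers, and arm as a mere covariate would not separate the two kinds of marker.

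The size of the problem can fairly be disputed. The correlations are assumed, the rates fall sharply at a voxel-type threshold, and a marker of sham response alone is not picked up if only the real arm is analysed. The 86% is also power to find a genuine association with outcome; the error lies in calling it prediction of response to rTMS. All of this stands, and it is why the consequence is stated as possible and not certain.

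The sentence that calls imaging changes predictors is largely editorial. The Synopsis separates baseline imaging, used for prediction, from pre-post comparison, used to characterise effects, and 9.4.3 says baseline. The loose sentence needs aligning, but it does not show an intention to predict response from post-treatment data.

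Finally, this is the last of six secondary hypotheses in a study that calls itself an exploratory pilot (5.5, 9.2), and the proposed test has little power at this size. Both points lower the severity. Neither makes a test without an arm contrast an answer to hypothesis 6.

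**Conclusion.** The point holds in a limited form. Section 9 specifies no arm term, marker-by-arm term or sham contrast for hypothesis 6, so no result from the stated model could distinguish a marker of rTMS response from a marker of course. As written the analysis yields no marker at all, because baseline HCS is constant. The mislabelling risk arises if the outcome alone is corrected. It is then about 41-86% pooled or 25-64% in the real arm for a single prognostic marker at p < 0.05, and about 5-37% pooled at p < 0.001. These figures rest on assumed correlations of 0.3 to 0.5, 20 evaluable patients per arm and a 0.9 SD treatment difference.

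The primary efficacy comparison is not affected. This should be fixed, together with the baseline-HCS correction, but it is not a bar to running the trial.

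**What to change.** In 9.4.3, replace the regression on baseline HCS with a model of post-treatment HCS on arm, baseline marker and arm-by-marker, and say which of the two post-treatment ratings is used. State that any claim of predicting response to rTMS rests on the arm-by-marker term, that this analysis is exploratory, and that marker main effects are reported as prognostic. In the Synopsis and section 3, reword the sentence about imaging changes so that baseline measures are the predictors, in line with the Synopsis objectives and 9.4.3; pre-post changes can be reported as correlates.

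This is a change of text only and needs no new data. The price is power: about 34-65% at p < 0.05, and about 4-15% at p < 0.001, for a marker acting only under real rTMS at assumed r = 0.5-0.7. The plan should say so, so that a null interaction is not read as evidence that no predictive marker exists.

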Based on this, we aim to assess the safety and efficacy of open-label accelerated rTMS, delivered over one day with four sessions, in first-episode schizophrenia patients who suffer from AVH and who decline first-line treatment with antipsychotic medication. We aim to further investigate the predictive value of cerebral blood flow, following the promising results of Homan et al. (2012), in first-episode schizophrenia patients.

In this project, we propose a translational approach to take the basic knowledge about the neurobiological underpinnings of AVH into direct clinical use, in a study of therapeutic outcome and related neurobiological changes and predictors of AVH.

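### Hypothesis 6 claims that baseline imaging predicts rTMS response, but the only planned method is an in-sample voxel-wise search aimed at a constant outcome

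*Combined protocol and SAP*

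**What the plan says.** Prediction is a stated goal in several places. The trial's title refers to prediction markers. Section 9.1, secondary hypothesis 6, has as its alternative: "There are specific neurophysiological markers that predict response to rTMS". Section 2.1 adds: "We aim to further investigate the predictive value of cerebral blood flow".

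The method is in Section 9.4.3. The aim and the means are given together: the plan is to "test if baseline neuroimaging biomarkers can predict response to rTMS. Therefore, voxel-wise multiple regression analyses in our neuroimaging measures will be performed". The purpose of that regression is "to reveal areas and networks which correlate with the baseline scores of the HCS". The same section goes on to ICA, seed-based connectivity, tract-based statistics, voxel-based morphometry and cortical thickness, using perfusion, resting fMRI, T1 and diffusion data.

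Three other places bear on this:

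- Section 3 says of the patient's baseline description of the voices, "which will be assigned a score of 10".
- Section 8.1 does define response: "Clinically significant improvement is defined as a score of <8 on the HCS".
- Section 9.3 names one analysis set, the patients who completed both scans and interviews and all four sessions.

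No section mentions a hold-out set, cross-validation, an optimism correction, external validation or any out-of-sample accuracy measure.

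**The concern.** There are two gaps between the claim and the method, and the first comes before the second.

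1. The regression named in Section 9.4.3 relates imaging to the baseline HCS, not to response. It cannot address hypothesis 6.
2. If the outcome is put right, the plan would still find the markers and judge their strength in the same patients. The sample correlation at a location picked because it was large does not estimate how well that location would predict a new patient. This is distinct from the false-positive rate. A real marker that survives full correction is still overstated, because only large sample correlations get through.

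At stake is how the conclusion on hypothesis 6 is worded and any number attached to it. Section 9.2 presents the trial as a possible basis for a larger study. An in-sample figure read as predictive accuracy would mislead the planning of any biomarker component of that study.

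**Working it through.** **Inputs from the plan.** 40 patients, 20 per arm, alpha 5% (Sections 9.2 and 9.4.1); one completer set (9.3); four imaging modalities (4.1); baseline HCS of 10 (3).

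**The plan's own figure.** The only sample size given is for the primary comparison: effect size 0.9, 80% power, 40 patients. An exact two-sided t test gives 20.39, so 21 per arm (42 in total), and 79.2% power at 20 per arm. The stated 40 reproduces within two patients. The plan gives no power or accuracy figure for the prediction aim, so everything below the next step is illustrative.

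**Step 1: the regression as written.** Baseline HCS is 10 for all patients, so its variance is 0. With r = cov(x, y) / (SDx × SDy), both numerator and denominator are 0. On whichever side of the model the HCS stands, no association can be estimated.

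**Step 2: substitute a response outcome.** Assumptions: normal data, M effective independent tests, two-sided Bonferroni at 0.05/M, true correlation ρ. Take n = 20 for the real-rTMS arm alone and n = 40 for both arms pooled. A marker is reported if |r| exceeds

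r_crit = t / √(n − 2 + t²), where t is the 1 − 0.05/(2M) quantile on n − 2 degrees of freedom.

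For M = 500:

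- n = 40: t = 4.346, r_crit = 4.346/√(38 + 18.89) = 0.576
- n = 20: t = 4.966, r_crit = 4.966/√(18 + 24.66) = 0.760

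With ρ = 0.40 (true R² 0.16), the mean R² among samples that pass is 0.39 at n = 40 (0.39/0.16 = 2.4 fold) and 0.63 at n = 20 (0.63/0.16 = 3.9 fold). Such a marker passes in only about 8% and 1% of samples.

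**Step 3: vary the assumptions.** Two million simulated samples per cell. Inflation is the mean r² among samples that pass, divided by ρ².

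| n | M | r_crit | Inflation, ρ = 0.3 | ρ = 0.4 | ρ = 0.5 | Passes, ρ = 0.4 |
|---|---|---|---|---|---|---|
| 40 | 100 | 0.525 | 3.66 | 2.15 | 1.47 | 17.2% |
| 40 | 1,000 | 0.596 | 4.44 | 2.56 | 1.70 | 5.8% |
| 40 | 10,000 | 0.653 | 5.15 | 2.94 | 1.92 | 1.7% |
| 20 | 100 | 0.706 | 6.21 | 3.53 | 2.30 | 3.3% |
| 20 | 1,000 | 0.780 | 7.26 | 4.11 | 2.65 | 0.6% |
| 20 | 10,000 | 0.834 | 8.11 | 4.57 | 2.93 | 0.1% |

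A stricter correction raises the threshold and therefore the inflation. With one pre-specified marker tested at 5% (M = 1) and ρ = 0.40, the inflation falls to 1.36 at n = 40 and 2.06 at n = 20, and the marker passes in 74% and 43% of samples.

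**Step 4: out-of-sample check, M = 1,000.** With no true marker, the best one shows a mean in-sample R² of about 0.27 (n = 40) or 0.49 (n = 20). Leave-one-out R² with the marker re-selected in each fold is roughly −0.3 to −0.4 and −0.5 to −0.8, depending on the reference mean and the simulation run. With one true marker of r = 0.40 among the 1,000, the nested R² is still negative: −0.27 and −0.74 in one run.

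**The case against.** **The trial is an exploratory pilot.** Sections 5.5 and 9.2 say so, and this lowers the stakes. It does not remove the point: prediction is a formal secondary hypothesis, and Section 9.4.9 (exploratory analyses) is marked not applicable.

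**The wording of the method is associational.** Section 9.4.3 speaks of areas that correlate, and predict is often used loosely for a baseline association. This stands in part. A reader might infer that the trial will publish an inflated predictive accuracy. The documents do not support that: none of them promises a peak r, an R², an accuracy figure or a patient-selection rule. The sentence in Section 9.4.1 on effect sizes and clinical importance is general and does not name imaging.

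**Some candidates are fixed in advance.** Section 9.4.3 pre-specifies superior temporal regions and the medial geniculate body, and Section 2.1 singles out cerebral blood flow. So it would be too strong to say that every marker is picked from the data. However, those regions then seed a search over other cortical areas, and the regressions are voxel-wise. The Section 2.1 text is weak support either way, since it also describes an open-label study.

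**Multiplicity may be controlled.** A permutation tool is named for the diffusion analysis only. No correction is stated elsewhere, so the statement about familywise correction is conditional. Permutation tests significance; it does not estimate out-of-sample accuracy.

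**Cross-validation has little power here.** This stands. Step 4 shows that with a wide search a real marker of moderate size would usually go undetected. It limits what can be claimed and does not justify using the in-sample figure instead.

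**Conclusion.** The point holds, and it comes second to correcting the outcome. Read literally, the regression in Section 9.4.3 yields no measure of response at all, so it would be wrong to say that the plan as written produces inflated prediction. Once a response outcome is used, as hypothesis 6 requires, the analysis supports statements of association and does not measure prediction.

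The direction of the bias does not depend on the assumptions; its size does. For true r of 0.3 to 0.5 and 100 to 10,000 effective tests, R² among surviving markers is inflated about 1.5 to 5 fold at n = 40 and 2.3 to 8 fold at n = 20. These figures are conditional on survival, which is uncommon in most of these settings (about 8% and 1% for r = 0.40 and 500 tests). The documents fix neither the number of effective tests nor any true correlation, so no single figure should be quoted as the bias of this trial. The n = 40 figures are for a correlation pooled over arms, which reflects prognosis; a difference between arms would be estimated less precisely. The primary endpoint is not affected.

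**What to change.** Amend Section 9.4.3 as follows, in this order.

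1. **Outcome and arm.** Replace the baseline HCS as regression target with the post-treatment HCS, and say which of the two post-baseline ratings is used. Include a marker-by-arm term, or state that the analysis is confined to the real-rTMS arm. The interaction is preferable, because a correlation pooled over arms, or seen in one arm only, does not separate response to rTMS from prognosis.
2. **Reporting.** Present the voxel-wise maps as associations. Do not report a peak-voxel r or R² as predictive strength. Word the conclusion on hypothesis 6 as association.
3. **Prediction claims.** Allow a claim of predictive value only from cross-validation in which selection and fitting are repeated inside every fold, with the out-of-sample R² and a permutation p-value. Preferably limit the candidates to a small pre-specified set, such as the regions already listed in Section 9.4.3 and cerebral blood flow.

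The cost is one SAP paragraph, a matching edit to hypothesis 6 and some computing time; no new data or patients are needed. Any accuracy reported will be lower and imprecise. The text should also say that, with 20 to 40 patients, a null cross-validated result does not show that no marker exists.
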